In case of significant clinical activity in any of the tumor-specific expansion cohorts, further patients may be added to enroll up to approximately 45 patients per cohort to further characterize the safety and explore preliminary clinical activity of LY2875358 in combination with a fixed regimen of ramucirumab treatment, if deemed appropriate after discussion and mutual agreement between the investigators and the sponsor. A sample size of 45 would give us a weighted average power of 83% based on 2-sided type 1 error rate of 5% to detect the significant dependence between biomarker status and clinical response as above. The criterion of significant clinical activity may vary based on tumor-specific response rates or landmark disease control. [Table JTBF.1](#) summarizes the parameters of Simon's optimal two-stage design for each cohort. The uninteresting RR of Gastric/GEJ, HCC, RCC are referenced from previous trials JVBD, JVBD and JVBP. The uninteresting RR of NSCLC is based on the RR in the second-line docetaxel arm (Scagliotti et al. 2011). Alternatively, disease control may be considered in order to proceed with enrollment up to 45 patients per cohort if deemed appropriate. [Table JTBF.2](#) summarizes landmark disease control and landmark disease control considered of interest to enroll up 45 patients per cohort. Such decisions will be documented in writing following discussions between the investigators and the sponsor, and a written notification will be sent to the IRB prior to enrollment of further patients.

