**Table JTBF.1. Simon's Optimal Two-stage Design Parameters for Each Cohort**

Tumor Type	Uninteresting RR	Favorable RR	1-sided type 1 error rate	Power	$n_1$	n	$r_1$	r
Gastric/GEJ	3%	10%	0.15	0.7	14	45	1	3
HCC	10%	22%	0.1	0.75	14	42	2	7
RCC	5%	12%	0.15	0.7	13	45	1	4
NSCLC	8.5%	22%	0.1	0.8	14	41	2	6

Abbreviations: GEJ = gastroesophageal junction; HCC = hepatocellular carcinoma;  $n_1$  = number of patients enrolled in the first stage; n = total number of patients enrolled; NSCLC = non-small cell lung cancer;  $r_1$  = number of responses required to proceed to the second stage; r = total number of responses required for further investigation of the drug; RCC = renal cell carcinoma; RR = response rate.

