6.11.3. Deaths, Other Serious Adverse Events, and Other Notable Adverse Events	20
6.11.4. Clinical Laboratory Evaluation	20
6.11.5. Vital Signs and Other Physical Findings	21
6.11.6. Electrocardiograms	21
6.11.7. Transfusion Data	21
6.11.8. X-Ray Data	21
6.12. Efficacy Analyses	21

6.13. Bioanalytical and Pharmacokinetic/Pharmacodynamic Methods.....	23
6.13.1. PK/PD Analyses.....	23
6.13.2. Biomarker Analyses	23
6.14. Subgroup Analyses.....	24
6.15. Protocol Violations.....	24
6.16. Interim Analyses and Data Monitoring	25
6.17. Planned Exploratory Analyses.....	25
6.18. Annual Report Analyses.....	25
6.19. Clinical Trial Registry Analyses	26
7. References	28

Table of Contents

Table	Page
Table JTBF.5.1. Multiple cohorts testing characteristics: Comparisons of chance of observing at least 1 patient with a clinical response between combination of ramucirumab and LY2875358 and ramucirumab monotherapy cohorts	11
Table JTBF.5.2. Previously Observed Antitumor activities of Ramucirumab Monotherapy on Gastric or GEJ adenocarcinoma, Hepatocellular carcinoma, and Renal cell cancer	11
Table JTBF.6.1. Data Handling Conventions and Rules	13

Table of Contents

Figure		Page
Figure JTBF.5.1. Study design for I4C-MC-JTBF.....		8

3. Revision History

This is the second version and was written to include a new cohort of NSCLC in Part B and provide further statistical justification in Section 5.2 Determination of Sample Size. SAP version 2 is approved before any interim analyses in Part B are conducted.

The key changes of the second version are:

- In Section 5.2, sample size is updated due to the addition of NSCLC cohort. Weighted average power is calculated to further justify the clinical utility of the biomarker. Table JTBF 5.3 is added to show the operating characteristics of Simon's optimal two-stage design, which provides details when further patients may be added to enroll up to approximately 45 patients per cohort.
- More details about the definition of PFS are provided in Section 6.12.

4. Study Objectives

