In case of significant clinical activity in any of the tumor-specific expansion cohorts, further patients may be added to enroll up to approximately 45 patients per cohort to further characterize the safety and explore clinical activity of LY2875358 in combination with a fixed regimen of ramucirumab treatment, if deemed appropriate after discussion and mutual agreement between the investigators and the sponsor. A sample size of 45 would give us a weighted average power of 83% based on 2-sided type I error rate of 5% to detect the significant dependence between biomarker status and clinical response as above. The criterion of significant clinical activity may vary based on tumor-specific response rates or landmark disease control. Table JTBF 5.2 summarizes the parameters of Simon's optimal two-stage design for each cohort. The uninteresting RR of Gastric/GEJ, HCC, RCC are referenced from previous trials JVBD, JVBPQ and JVBP (Fuchs et al. 2013). The uninteresting RR of NSCLC is based on the average RR of squamous and nonsquamous groups in the second-line docetaxel arm (Scagliotti et al. 2011). Alternatively, disease control may be considered in order to proceed with enrollment up to 45 patients per cohort if deemed appropriate. Table JTBF 5.3 summarizes landmark disease control and landmark disease control considered of interest to enroll up 45 patients per cohort. Such decisions will be documented in writing, and a written notification will be sent to the IRB prior to enrollment of further patients.

Table JTBF.5.2. Simon's Optimal Two-stage Design Parameters for Each Cohort

Tumor Type	Uninteresting RR	Favorable RR	1-sided Type I Error Rate	Power	n ₁	n	r ₁	r
Gastric/GEJ	3%	10%	0.15	0.7	14	45	1	3
HCC	10%	22%	0.1	0.75	14	42	1	7
RCC	5%	12%	0.15	0.7	13	45	1	4
NSCLC	8.5%	22%	0.1	0.8	14	41	2	6

Abbreviations: GEJ=gastroesophageal junction; HCC=hepatocellular carcinoma; n₁=number of patients enrolled in the first stage; n=total number of patients enrolled; NSCLC=non-small cell lung cancer; r₁=number of responses required to proceed to the second stage; r=total number of responses required for further investigation of the drug; RCC=renal cell carcinoma; RR=response rate.

Table JTBF.5.3. Previously Observed Antitumor activities of Ramucirumab Monotherapy on Gastric or GEJ adenocarcinoma, Hepatocellular carcinoma, and Renal cell cancer

Tumor Type	Study	n	mPFS	mOS	ORR	DCR	Landmark	Secondary CSF
Gastric/GEJ	JVBD	355	2.1mos	5.2 mos	3%	49%	12-wks PFS 40%	60%

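### HCC stage-1 expansion threshold is 2 responses in the protocol and 1 in the SAP; at the tabulated design only 2 keeps the stated 0.10 type I error

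*SAP*

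**What the plan says.** Protocol Section 8.1.1 and SAP Section 5.2 each tabulate a Simon optimal two-stage design per tumor cohort, as a guide to when a cohort may grow from about 15 to about 45 patients.

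- Protocol Table JTBF.1, HCC row: "HCC 10% 22% 0.1 0.75 14 42 2 7"
- SAP Table JTBF.5.2, HCC row: "HCC 10% 22% 0.1 0.75 14 42 1 7"

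The columns are uninteresting response rate (RR), favorable RR, one-sided type I error, power, n1, n, r1 and r. The rows agree in everything except r1. The gastric/GEJ, RCC and NSCLC rows are identical in the two tables.

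Both footnotes define r1 as the "number of responses required to proceed to the second stage" and r as the "total number of responses required for further investigation of the drug". Both are therefore minimum counts: at least r1, then at least r.

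The tables are not a binding rule. Protocol Section 8.1.1 adds: "The criterion of significant clinical activity may vary based on tumor-specific response rates or landmark disease control". The SAP revision history says: "SAP version 2 is approved before any interim analyses in Part B are conducted".

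**The concern.** One threshold cannot be both 1 and 2 under the same definition. The disputed result is exactly one response among the first 14 HCC patients: it meets the SAP threshold and misses the protocol threshold.

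The SAP value also looks odd within its own table. The NSCLC row, "NSCLC 8.5% 22% 0.1 0.8 14 41 2 6", has the same n1 and the same favorable RR as HCC and a lower uninteresting RR (8.5% against 10%), yet it asks for 2 responses where HCC asks for 1. The two rows differ in power, n and r as well, so this is an anomaly, not a contradiction.

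At stake is how well the first HCC look screens. ORR is the co-primary objective for Part B, and a threshold of 1 lets most cohorts with an uninteresting response rate through. If the mismatch is resolved only after the HCC responses are known, the choice of threshold will look driven by the data.

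**Working it through.** **Inputs** (HCC rows of both tables): p0 = 0.10, p1 = 0.22, one-sided type I error 0.10, power 0.75, n1 = 14, n = 42, r = 7, and r1 = 2 (protocol) or 1 (SAP). The second stage has 42 − 14 = 28 patients.

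**Formulas.** Let X1 ~ Bin(14, p) and X2 ~ Bin(28, p).

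- P(meet stage-1 threshold) = P(X1 ≥ r1)
- P(success) = Σ over x ≥ r1 of P(X1 = x) · P(X2 ≥ 7 − x). This is the type I error at p0 and the power at p1.
- Expected N at p0 = 14 + 28 · P(X1 ≥ r1 | p0)

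**The plan's own figures first.** Both documents give a 79% chance of at least one response among 15 patients at a true RR of 10%: 1 − 0.9^15 = 0.794, which agrees. The three undisputed rows, read as at least r1 and at least r, also reproduce:

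| Row | Type I error (stated) | Power (stated) |
|---|---|---|
| Gastric/GEJ | 0.110 (0.15) | 0.701 (0.7) |
| RCC | 0.149 (0.15) | 0.701 (0.7) |
| NSCLC | 0.097 (0.1) | 0.806 (0.8) |

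Each is also the optimal design found by search under that reading, so the footnote definition is the one the tables use.

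**HCC, stage 1.**

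- At p0: P(X1 = 0) = 0.9^14 = 0.2288 and P(X1 = 1) = 14 · 0.1 · 0.9^13 = 0.3559.
- r1 = 1: 1 − 0.2288 = 77.1%.
- r1 = 2: 1 − 0.2288 − 0.3559 = 41.5%.
- At p1 = 0.22, P(X1 = 1) = 12.2%. The threshold is met with probability 96.9% (r1 = 1) or 84.7% (r1 = 2).

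**HCC, whole design.** The two rules differ only on the path with X1 = 1, which then needs at least 6 of 28.

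- At p0 that path adds 0.3559 · 0.0550 = 0.0196, so type I error goes from 0.0978 to 0.1174.
- At p1 it adds 0.1218 · 0.6025 = 0.0734, so power goes from 0.7606 to 0.8340.
- Expected N at p0: 14 + 28 · 0.4154 = 25.6 for r1 = 2, and 14 + 28 · 0.7712 = 35.6 for r1 = 1.

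| HCC | Type I error | Power | P(meet threshold at 10%) | Expected N at 10% |
|---|---|---|---|---|
| r1 = 2 (protocol) | 0.098 | 0.761 | 41.5% | 25.6 |
| r1 = 1 (SAP) | 0.117 | 0.834 | 77.1% | 35.6 |

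**Which value is the Simon optimum?** A search over n up to 55 with type I error ≤ 0.10 and power ≥ 0.75 returns n1 = 14, n = 42, r1 = 2, r = 7 (expected N 25.63; next best 25.77). The best design with r1 = 1 is n1 = 9, n = 40, r = 7 (expected N 27.99), not 14/42.

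**Could a different convention explain the SAP value?**

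- Strictly more than r1 and strictly more than r: HCC power is 0.675, below 0.75.
- Strictly more than r1, but at least r: HCC with r1 = 1 becomes 0.098/0.761, but power falls to 0.611 for NSCLC (stated 0.8), 0.447 for RCC and 0.406 for gastric/GEJ (stated 0.7).

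No single convention makes every row of the SAP table work. A likely origin of the 1 is the classical stop-if-at-most notation carried into that one cell.

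**Sensitivity.**

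| Setting | Type I error, r1 = 2 | Type I error, r1 = 1 | P(meet threshold), r1 = 2 | P(meet threshold), r1 = 1 |
|---|---|---|---|---|
| Tabulated 14/42, null 10% | 0.098 | 0.117 | 41.5% | 77.1% |
| Look at 15, total 42 | 0.102 | 0.118 | 45.1% | 79.4% |
| Look at 15, total 45 | 0.128 | 0.153 | 45.1% | 79.4% |
| 14/42, null 4/42 = 9.5% | 0.080 | 0.097 | 39.1% | 75.4% |

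The 4/42 is the response count from the first-line HCC study of ramucirumab monotherapy, in protocol Section 5.2.1.2.

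**The case against.** The best case against concerns weight, since the mismatch itself cannot be disputed.

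First, the threshold is not a test. Analyses are descriptive, ORR is reported with a Clopper-Pearson interval, Part B is only likened to the first stage of a Simon design, expansion needs agreement between sponsor and investigators, and disease control is an alternative route. Type I error, power and expected N then describe a mechanical rule that the plan does not impose. This stands, and it limits the consequence: neither value forces or forbids expansion.

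Second, the type I error argument depends on the exact tabulated design. With the look at 15 patients, r1 = 2 also misses 0.10 slightly (0.102). With 15 then 45, both values miss it. With the unrounded null of 4/42, both meet it. This stands too. The stage-1 gap, however, stays at about 34 to 36 percentage points in every setting.

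Third, both documents say generally that one response in about 15 might warrant further study. That remark is not specific to HCC, and its contrast is a true RR of 10% against one near 3%. For HCC, 10% is the uninteresting rate, so the documents' own 79% becomes the chance that an uninteresting cohort passes. It does not support r1 = 1 here.

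Fourth, the current protocol (approved March 2015) is later than the SAP (November 2014) and carries 2. That favors 2, but neither document says which prevails. The amendment (b) summary lists no change to Section 8.1.1; as it also mentions unspecified editorial changes throughout, that silence is weak evidence.

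**Conclusion.** The concern holds. The two documents give different HCC stage-1 thresholds under one definition, and the SAP value is the wrong one by the table's own parameters. At n1 = 14, n = 42, r = 7 and a null of 10%, r1 = 1 gives type I error 0.117 against the stated 0.10, while r1 = 2 gives 0.098 with power 0.761 and is the Simon optimum. Only 2 here means of the two printed values: r1 = 3 would also hold the type I error (0.061), but with power 0.589.

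The type I error excess is small and depends on rounding the null to 10%. The effect that survives every variation tried is at the first look: 77.1% against 41.5% of cohorts with a true RR of 10% would meet the threshold. The disputed outcome, one response in 14, has probability 35.6% at that rate. The figure of 10 extra expected patients (35.6 against 25.6) applies only if the threshold is followed mechanically. This should be fixed, but it does not undermine the design.

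**What to change.** In SAP Table JTBF.5.2, change r1 in the HCC row from 1 to 2, to match protocol Table JTBF.1. Do this, with a dated entry in the SAP revision history, before the HCC interim analysis.

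The cost is one table cell. Sample sizes, the final threshold of 7, the stated error rates and the other three cohorts stay as they are. Computed HCC power falls from 0.834 to 0.761, still above the stated 0.75, and the chance that a cohort at the favorable RR of 22% meets the first threshold falls from 96.9% to 84.7%. That loss is the one the protocol's design already accepts.

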5.3. Method of Assignment to Treatment

Patients who meet all criteria for enrollment will be assigned to receive ramucirumab and LY2875358 in this study. Before each patient's enrollment into the study, an eligibility check must be conducted between the investigational site and the Lilly clinical research personnel to confirm that each patient meets all enrollment criteria. Upon confirmation of eligibility, the sponsor will confirm the dose and identification number assignment and cohort for each patient. No dose escalations (ie, to the next cohort) can occur without prior discussion and agreement with the responsible Lilly CRP or CRS.

If investigators have eligible patients who have consented concurrently to Part A, more than 3 patients may be entered at a particular dose level, provided that accrual has not ceased due to excessive toxicity. This enrollment procedure is allowed because of the advanced disease state of this patient population and the screening involved in defining eligibility. This event should be approved by the sponsor following discussions with the investigators.

6. A Priori Statistical Methods

6.1. General Considerations

Statistical analysis of this study will be the responsibility of Lilly. The interpretation of the study results will be the responsibility of the investigator with the Lilly Clinical Research Physician (CRP), pharmacokineticist, statistician and clinical development associate. The Lilly CRP and statistician will also be responsible for the appropriate conduct of an internal review process for both the final study report and any study-related material to be authorized for publication by Lilly.

The analyses for this study will be descriptive, except for possible exploratory analyses as deemed appropriate. Data analyses will be provided by dose levels and for all patients combined wherever appropriate. For continuous variables, summary statistics will include number of patients (N), mean, median, standard deviation (SD), standard error (SE), minimum, and maximum. Categorical endpoints will be summarized using N, frequency, percentages, and associated SE.

Exploratory analyses of the data that are not described in the protocol will be conducted as deemed appropriate.

In Part A, all data will be summarized by cohort (and all patients combined when appropriate), unless stated otherwise. In Part B, all data will be summarized by tumor-specific cohort.

Any change to the data analysis methods described in the protocol will require an amendment ONLY if it changes a principal feature of the protocol. Any other change to the data analysis methods described in the protocol and the justification for making the change will be described in the clinical study report.

Table JTBF.6.1. explains the data handling conventions and rules used in the analysis:

Table JTBF.6.1. Data Handling Conventions and Rules

Term	Definition or Rule
Study Day	If assessment is on or after date of first dose then (date of assessment) – (date of first study drug dose) +1
	If assessment precedes first dose of drug then (date of assessment) – (date of first study drug dose)
	There is no study day 0. Study day 1 is the date of first dose and study day -1 is the day before the first dose.
Cycle Day	If assessment is on or after date of first dose in the cycle then (date of assessment) – (date of first study drug dose in cycle) +1
	If assessment precedes first dose of drug in a cycle then (date of assessment) – (date of first study drug dose in cycle)
	There is no cycle day 0. Cycle day 1 is the date of first dose in the

	cycle and cycle day -1 is the day before the first dose.
Baseline	For change from baseline analyses, baseline value is defined as the last reported measure on or before the first dose (prior to the dose administration). For change from baseline within a cycle, the measure prior to the first dose of that cycle is baseline. If more than one pre-dose measure is available, they may be averaged if appropriate.
Entered	Patients who sign the informed consent document.
Enrolled	Patients who have been assigned to a treatment (assigned means they received ≥ 1 dose for this study).

